We will study 20 subjects a total of 2 times at least a week apart in random order. All subjects will be admitted to the Mayo Clinic CRTU at 1700 hours the evening before the study. Women who could become pregnant will have a urine collection for point of care pregnancy testing. Following ingestion of a standard 10 kcal/kg caffeine-free meal, subjects will fast overnight. The following morning at approximately 0530 (-210 min), a dorsal hand vein will be cannulated and placed in a heated Plexiglas box maintained at 55°C to allow sampling of arterialized venous blood. The contralateral forearm vein will be cannulated for glucose, and hormone infusions. At approximately 0600 (-180 min), a primed, (10 $\mu$ Ci prime, 0.1 $\mu$ Ci/min continuous) infusion containing trace amounts of glucose labeled with [3-H] glucose will be started and continued till 0900 (0 min). Subsequently, the infusion will be varied so as to mimic the anticipated pattern of fall of EGP to minimize changes in Specific Activity. At that time another glucose infusion, also labeled with [3-H] glucose will commence and infusion rate varied so as to produce peripheral glucose concentrations of ~160mg/dL. A glucagon infusion at 0.4ng/Kg/min will start at 0900 (0 min), increasing by 0.2ng/kg/min every hour (**Fig.3**). Blood will be sampled till the end of the study (1400 – 300 min) when I.V. cannulas will be removed; participants will consume a late lunch and leave the CRTU. This will be referred to as the saline (**Sal**) day because 0.9% Saline will be infused between 0 and 300 min. On another study day, exendin-9,39 (**Exe**) will be infused at 300pmol/kg/min between 0 and 300 min.

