**Analytical Techniques:** All blood will be immediately placed on ice, centrifuged at 4°C, separated and stored at -80°C until assay. Glucose will be measured using a Yellow Springs glucose analyzer. Glucagon will be collected in protease inhibitor-containing tubes (BD800, BD Franklin Lakes, NJ) and measured using an ELISA (Mercodia, Winston-Salem, NC). C-peptide will be measured using EMD Millipore (Billerica, MA) reagents. Insulin will be measured using a chemiluminescence assay with reagents obtained from Beckman (Access Assay, Beckman, Chaska, MN). Total and Intact GLP-1 will be collected in protease inhibitor-containing tubes (BD800, BD Franklin Lakes, NJ) and measured using an ELISA (ALPCO Diagnostics, Salem, NH). [3-H] glucose specific activity will be measured by liquid scintillation counting after deproteinization and passage over anion- and cation-exchange columns.

**Calculations:** In addition to fasting, peak and nadir hormone concentrations, we will calculate area above basal (AAB) or area under the curve (AUC) during the experiment using the trapezoidal rule as previously described.  $S_i$ , Insulin Secretion Rate (ISR) and  $\beta$ -Cell responsivity ( $\Phi$ ) indices will be calculated from the glucose, insulin and C-peptide concentrations observed during the experiments using the minimal model, incorporating age-associated changes in C-peptide kinetics.  $\Phi$  is derived from the sum of  $\phi_1$  (1st phase insulin secretion) and  $\phi_2$  (2nd phase insulin secretion) as before. Disposition index (DI) will express  $\beta$ -cell function as a function of the prevailing insulin action. Glucose disappearance (Rd) will be calculated using steady state Steele equations after Specific activity is smoothed as previously described. Endogenous glucose production (EGP) will be calculated as the difference between the tracer determined rate of glucose appearance and the glucose infusion rate. All infusion rates will be expressed as Kg per lean body mass.

Power Calculation	Mean $\pm$ SD	Detectable difference
1° hypothesis (n = 20 - paired)		
$\Phi$ (10 $^{-9}$ min $^{-1}$ ) - hyperglycemia	149 $\pm$ 45	30 (20%)

Table 1: Means  $\pm$  SD used to estimate power

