**Statistical Analysis:** A paired 2-tailed student *t*-test (parametric) or a Wilcoxon rank-sign test (non-parametric) will be used to examine differences between **Sal** and **Exe** days for the 1° hypothesis (**Table 3**).

**3) Power Calculation:** Please refer to **Table 3**.

**3) Interpretation:** If glucagon stimulates insulin secretion by acting, at least partially, through GLP1R we would expect that exendin-9,39 will decrease the response to glucagon by blocking GLP1R. To test our 1° hypothesis, we will compare  $\Phi$  during each glucagon infusion rate in the presence and absence of exendin-9,39. Assuming that glucagon concentrations as encountered in the islet are necessary to stimulate insulin secretion via GLP1R, we expect differences to be more marked at the higher glucagon infusion rates (2° hypothesis). The experiments will be conducted in relatively lean, healthy and insulin sensitive humans. Under these experimental conditions, we expect EGP to be suppressed and insulin secretion stimulated by hyperglycemia and glucagon infusion. The rising infusion rates of glucagon will enable us to examine the

effects of the latter on endogenous glucose production (EGP) and endogenous insulin secretion in the presence and absence of GLP1R blockade.

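### Day order is randomised without stated balancing and the primary paired test has no period term, so any visit effect would shift the realised estimate or widen its error

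*Combined protocol and SAP*

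**What the plan says.** The study-day text in Section IV (Research Design and Methods) sets up a two-visit crossover: "We will study 20 subjects a total of 2 times at least a week apart in random order". One visit is the saline day, so named "because 0.9% Saline will be infused between 0 and 300 min". The other is the active day: "On another study day, exendin-9,39" is infused over the same interval. The text gives no block, ratio or counterbalancing for the order.

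The Statistical Analysis paragraph names one analysis for the primary hypothesis: "A paired 2-tailed student *t*-test (parametric) or a Wilcoxon rank-sign test (non-parametric) will be used to examine differences between" the saline and exendin days. The Interpretation paragraph says that Φ is compared "during each glucagon infusion rate in the presence and absence of exendin-9,39". No period, visit or sequence term appears anywhere in the document.

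The power table is headed "1° hypothesis (n = 20 - paired") and gives Φ as 149 ± 45 with a detectable difference of 30 (20%). The text refers to a Table 3, but the only power table is labelled Table 1, and I take that to be the one meant. Alpha, power, a dropout allowance and the type of SD are not stated.

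**The concern.** In a two-period crossover, anything that changes Φ between the first and second visit enters each within-subject difference with a sign set by the order. The paired test ignores that sign. If the two orders are unequal in number, part of the visit effect is left in the treatment estimate. If they are equal, the visit effect cancels from the mean but stays in the SD of the differences, so the test becomes conservative.

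The stated 30 units corresponds to almost exactly 80% power under the usual assumptions, and no dropout allowance is given. There is little spare power to absorb either effect. Both can be prevented at the design stage at almost no cost.

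**Working it through.** **Inputs.** From the documents: n = 20 pairs, Φ mean 149, SD 45, detectable difference 30, two-tailed test. Assumed, because not stated: alpha 0.05, power 80%, 45 is the SD of the paired differences, and no dropout. The visit effect p is also assumed, over 5 to 20 units (5/149 = 3% to 20/149 = 13% of the mean).

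**1. Reproducing the plan's figure.** The paired standard error is 45/√20 = 10.06 on 19 df. By the noncentral t distribution the detectable difference is 29.7, against the stated 30, and power at 30 is 80.7%.

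**2. How a visit effect enters.** If Φ changes by p from the first to the second day, each exendin-minus-saline difference shifts by +p (saline first) or −p (exendin first). With n1 and n2 subjects in the two orders, the mean difference shifts by p × (n1 − n2)/20.
- At 10/10 the shift is 0, and the SD of the differences becomes about √(45² + p²).
- At 13/7 the shift is p × 6/20 = 0.3p, that is 1.5 to 6 units for p = 5 to 20.

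**3. How likely imbalance is.** If order were set by simple randomisation (the method is not stated), Binomial(20, 0.5) gives exactly 10/10 in 17.6% of trials and 13/7 or worse in 26.3%.

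**4. The planned paired test.** Power is for a true difference of 30, by simulation. The 10/10 detectable difference uses the widened SD.

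| p | Detectable difference, 10/10 | Power, 13/7, shift opposes effect | Power, 13/7, shift favours effect | Type I error, 13/7 |
|---|---|---|---|---|
| 5 | 29.9 | 76% | 84% | 5.0% |
| 10 | 30.4 | 70% | 86% | 5.4% |
| 15 | 31.3 | 63% | 88% | 5.9% |
| 20 | 32.5 | 55% | 89% | 6.3% |

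Direct simulation of the 10/10 detectable difference gives slightly smaller values: 29.9, 30.3, 31.0 and 31.9. Power at 10/10 runs from 80.3% (p = 5) to 74.7% (p = 20). Type I error at 10/10 falls below 5%; at p = 15 it is 3.9%.

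**5. The period-adjusted test.** Average the two sequence means with equal weight. The standard error is 45 × 0.5 × √(1/n1 + 1/n2) on n1 + n2 − 2 df, and it does not depend on p.

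| Split | Detectable difference, adjusted |
|---|---|
| 10/10 | 29.8 |
| 12/8 | 30.4 |
| 13/7 | 31.3 |
| 10/9 | 30.7 (paired test, no visit effect: 30.6) |
| 9/9 | 31.7 (paired test, no visit effect: 31.5) |

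Adjusted power at 30 is 80.5% at 10/10 and 77% at 13/7, with type I error 5%.

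**6. If 45 already contains the visit effect.** The unadjusted detectable difference at 10/10 stays at 29.7. The adjusted one is 29.8 × √(1 − p²/45²), which falls from 29.6 (p = 5) to 26.7 (p = 20).

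**The case against.** The strongest reply is that the planned test is already valid. Order is randomised, and averaged over simple randomisation the paired test keeps its type I error at about 5% for every p considered. The 6.3% is conditional on a 13/7 split and the largest assumed p. This stands: the issue is a conditional shift and lost precision.

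Second, nothing in the documents shows that a visit effect exists. Diet, admission, evening meal, fast, clock times and target glucose are all standardised, so it may be small. This also stands. At 10/10 the adjusted test gains only 0.2 points of power at p = 5, about 1 point at p = 10 and under 6 points at p = 20.

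Third, the 55% needs an uneven split, the adverse direction and the largest p together. A split of 13/7 or worse in the adverse direction has probability 26.3%/2, about 13%. Averaged over simple randomisation, paired power is 80.3%, 78.8% and 73.3% for p = 5, 10 and 20, which is the fairer summary before the split is known.

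Fourth, a period term without blocking can cost power. Under simple randomisation adjusted power averages about 78%, and the paired test stays ahead until p is roughly 11 to 12 units. That argues for making both changes together.

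Fifth, the meaning of the SD matters more than the visit effect. If 45 is a between-subject SD, power at 30 runs from 52% to 95% for within-subject correlations of 0 to 0.7. This is true, but it is a separate matter and leaves the algebra of the period effect unchanged.

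Finally, random order is compatible with a blocked list, and the design figure could not be seen. The claim is therefore only that balancing is not stated. Balance alone would remove the shift but not the widened error.

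**Conclusion.** The concern holds as a low-cost improvement. The document states neither a balanced order nor a period term. If a visit effect exists, the paired test either carries part of it in the realised estimate (0.3p at 13/7) or carries it as noise (at 10/10, a detectable difference of up to 32.5 by formula, or 31.9 by simulation, against 29.8 adjusted). With no visit effect there is no gain.

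The sizes rest on an SD of differences of 45, two-sided alpha 0.05, 80% power and an assumed p of 5 to 20 units. I am confident of the omission and of the algebra; how much it matters in practice depends on a visit effect that the documents do not quantify. The design itself is not in question.

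**What to change.** Make two changes together.

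1. **Order.** State that order is allocated from a blocked list giving 10 saline-first and 10 exendin-first subjects.
2. **Analysis.** Make the primary analysis period-adjusted. Compute each subject's exendin-minus-saline difference in Φ, average the two sequence means with equal weight, and test on 18 df. A mixed model with treatment and period fixed and subject random is equivalent. For the non-parametric route, compare first-day-minus-second-day differences between the two orders with a Wilcoxon rank-sum test. Use the same form for Φ at each glucagon infusion rate, and keep the paired test as a sensitivity analysis.

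The cost is an allocation list, a short change to the analysis text and one degree of freedom. At 10/10 with no visit effect the detectable difference goes from 29.7 to 29.8, and power at 30 from 80.7% to 80.5%. Adding the period term without blocking is not advised: with simple randomisation and no visit effect it lowers average power from about 81% to 78%.

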**[name]**

**26th March 2020**

**IRB# 20-003995**

**NCT04459338**

## **Abstract**

Glucagon is an important insulin secretagogue in the concentrations found within the islet.  $\alpha$ -cell dysfunction as occurs in T2DM, in prediabetes or in response to FFA elevation results in increased glucagon concentrations. In these conditions glucagon signals through the GLP-1 receptor (GLP1R) present on  $\beta$ -cells but its net contribution to insulin secretion is unknown. In this experiment we will determine the contribution of GLP-1R signaling to glucagon-induced insulin secretion *in vivo*. To do so, we will use a dose-response experiment for glucagon-stimulated insulin secretion. The experimental conditions will then examine how glucagon-stimulated insulin secretion is modified by blockade of GLP1R blockade using exendin-9,39. This approach will complement other experiments using a glucagon bolus known to stimulate  $\beta$ -cell function in the presence and absence of GLP1R blockade.

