## **I. Hypothesis and Specific Aims**

Glucagon within the islet can signal the  $\beta$ -cell through GLP1R, and acts as an insulin secretagogue. This signaling is blocked by exendin-9,39. The relative importance of glucagon signaling through its cognate receptor or through GLP1R is unknown. Despite the lower affinity of GLP1R for glucagon, intra-islet concentrations of glucagon are sufficiently high to stimulate GLP1R^3. The other situation where this may occur is in response to pharmacologic doses of glucagon as used for  $\beta$ -cell function testing or raising peripheral glucagon concentrations above fasting values. **The experiments proposed will characterize the role of GLP1R in glucagon's actions on the  $\beta$ -cell and the potential therapeutic role of dual (GLP-1R and glucagon receptor) agonists for the treatment of T2DM and obesity.** The experiments will also provide an opportunity to test glucagon's actions on insulin secretion, independently of glucose concentrations.

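### A Sal–Exe difference in the level of Φ does not by itself show a reduced response to infused glucagon, and the rate-by-blockade comparison has no named test (should fix; inexpensive)

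*Combined protocol and SAP*

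**What the plan says.** Section I states one aim, the contribution of GLP1R to glucagon-stimulated insulin secretion. The 1° hypothesis is that exendin-9,39 decreases that secretion. The 2° hypothesis is that the contribution is larger at higher glucagon concentrations. The Abstract announces the design: "we will use a dose-response experiment for glucagon-stimulated insulin secretion".

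Section IV (description of the study days) has three infusions starting at 0 min: glucose, adjusted to about 160 mg/dL; glucagon at 0.4 ng/kg/min, rising by 0.2 each hour; and saline or exendin-9,39, to 300 min. That gives five glucagon steps (0.4, 0.6, 0.8, 1.0 and 1.2 ng/kg/min). The text describes no hyperglycaemic step without infused glucagon. Figure 3 is not reproduced in the copy reviewed, but the text fixes the timing.

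Section IV, Statistical Analysis, names a paired two-sided t-test or a Wilcoxon test for the 1° hypothesis only. Under Interpretation, Φ is compared "during each glucagon infusion rate in the presence and absence of exendin-9,39"; if glucagon acts partly through GLP1R, "we would expect that exendin-9,39 will decrease the response to glucagon by blocking GLP1R". The same paragraph expects "insulin secretion stimulated by hyperglycemia and glucagon infusion", so it recognises two stimuli. On the 2° hypothesis it says "we expect differences to be more marked at the higher glucagon infusion rates", and it adds that the rising rates will allow study of "endogenous insulin secretion in the presence and absence of GLP1R blockade". No test or model is attached to either statement. Table 1 has a power row for the 1° hypothesis only.

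**The concern.** The hypothesis concerns a response to glucagon. The named test concerns the level of Φ while glucose and glucagon act together. The two coincide only if exendin leaves secretion under glucose unchanged, and the plan's own background gives reason to doubt that:

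- Section II reports that exendin during a meal-like intravenous glucose challenge impaired β-cell function in non-diabetic people.
- Section II also mentions a cited hyperglycaemic-clamp study with an effect of GLP1R blockade under intravenous glucose alone. Its title in the Bibliography concerns type 2 diabetes.
- Section III shows the same direction in non-diabetic islets (n = 3 technical repeats).

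None of these gives the size of such an effect over 300 minutes at about 160 mg/dL. They make it plausible and no more.

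At stake is the conclusion of the study's single aim. With the plan followed exactly, the primary comparison could be positive with no change in the response to infused glucagon, and the text does not say how far the conclusion may then go. The comparison that bears more directly on the question, whether the Sal–Exe difference grows with rate, has no prespecified analysis. Separate paired tests at five rates do not supply one: significance at some rates and not at others is not a test that the differences differ.

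**Working it through.** **Inputs from the documents.** n = 20, paired; Φ 149 ± 45; detectable difference 30 (Table 1); five rates from 0.4 to 1.2 ng/kg/min.

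**Assumed, because the documents do not give them.** Two-sided 5% level; 80% power; 45 read as the SD of the paired Sal–Exe difference and applied at each step; the size and shape of any glucose-only effect; the correlation r of paired differences between steps.

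**1. The plan's own figure.** Paired t-test, 19 df, noncentrality = (difference/SD) × √20. For 30: (30/45) × √20 = 2.98, power 80.7%. The difference detectable with 80% power is 29.7, and 30/149 = 20%. Table 1 reproduces.

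**2. Level test when exendin acts only on secretion under glucose.** Same formula, one paired test:

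| SD of paired differences | 10 units | 20 units | 30 units |
|---|---|---|---|
| 45 | 16% | 47% | 81% |
| 53.2 (45 per day, between-day correlation 0.3) | 13% | 36% | 67% |
| 34.9 (45 per day, between-day correlation 0.7) | 23% | 68% | 95% |

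The last two SDs are 45 × √(2(1 − ρ)). With 30 units at every step and SD 45, simulation gives at least one positive result among the five per-rate tests in 93–99% of trials (step correlations 0.8 to 0.3).

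**3. Slope of the Sal–Exe difference over the five rates.** Code the steps −2 to 2 (sum of squares 10). The change over the full range (four steps) has SD 45 × √(1 − r) × 4/√10: 40.25 at r = 0.5 and 31.18 at r = 0.7. The change detectable with 80% power is 26.6 or 20.6 units. A constant effect contributes nothing, because the codes sum to zero, so the slope rejects at its nominal 5%.

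**4. Where the slope stops protecting.**

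- *Effect changing with time.* Take 15 units in hour 1 and 30 afterwards. Slope per step = (−2×15 − 1×30 + 0×30 + 1×30 + 2×30)/10 = 3, or 12 over the range. Rejection is 24.5% at r = 0.5 and 37% at r = 0.7. On the log scale (assumed SD of log differences 45/149 = 0.302, Sal Φ flat at 149) it is 32% and 49%.
- *Proportional effect with Φ rising on the Sal day.* For a 20% effect and a Sal rise of 50, 75 or 100 units, the raw difference grows by 0.2 × the rise = 10, 15 or 20 units. The raw slope rejects in 18%, 35% or 56% at r = 0.5, and 28%, 53% or 78% at r = 0.7. On the log scale a constant proportional effect cancels, and rejection returns to about 5%.

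Requiring both scales to agree therefore deals with the constant and the proportional case. It does not deal with an effect that changes over time.

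**The case against.** **The aim is wider than infused glucagon.** Neither the aim nor the hypotheses say infused, and Section I holds that "intra-islet concentrations of glucagon are sufficiently high to stimulate GLP1R". Part of what is called a glucose-only effect above could be intra-islet glucagon acting through GLP1R, which is within the aim. This stands. It narrows the rival explanation to endogenous GLP-1, which Section II itself suggests contributes to islet function outside the postprandial period. The level comparison cannot separate the two, and the Abstract and the Interpretation paragraph do frame the question as a dose-response to glucagon.

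**The level test is not read alone.** The plan expects a gradient with rate, and it mentions complementary bolus experiments (Abstract) and other work on endogenous GLP-1 in fasting and hyperglycaemic conditions (Section IV). This is fair as to intent. But that work gives no control within this trial, and the gradient has no named test. Nor does the common glucose target settle the matter: it equalises the stimulus on the two days, not exendin's effect on the response to it.

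**The remedy does not cure the problem.** Rates always ascend, so rate and elapsed time cannot be separated, and an effect already complete at the first step produces no slope. This stands too, and is why the contrast can only be supportive.

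**The numbers are hypothetical.** They are. A reader might take 81% as this trial's false-positive rate. The documents do not support that: 81% is simply the plan's power at its own detectable difference, and no source gives the size of a glucose-only effect or an SD for hourly Φ.

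**Conclusion.** The point holds as a limit on inference plus a gap in prespecification, and should be fixed. A positive Sal–Exe comparison supports the statement that GLP1R blockade lowers secretion during combined hyperglycaemia and glucagon infusion. It does not by itself show a reduced response to infused glucagon, and the 2° hypothesis has no named test.

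The logical point rests on the schedule and the named test, and is firm. Its practical size is unknown: the 16%, 47% and 81% depend on assumed effects of 10, 20 and 30 units and on reading 45 as the SD of paired differences, and the slope figures depend also on assumed step correlations.

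Two stronger readings are tempting. One is that the primary comparison is invalid, or that any difference found would be a glucose effect. The documents do not support it: they establish no such effect under this clamp, and some of it might belong to the aim. The other is that the slope test would settle attribution. It would not, as the time-varying case shows.

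**What to change.** Change Section IV, Statistical Analysis and Interpretation, only.

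1. State that the Sal–Exe level comparison supports a conclusion about secretion during combined hyperglycaemia and glucagon infusion, and does not alone establish a reduced response to infused glucagon.
2. For the 2° hypothesis, prespecify each subject's slope of the Sal–Exe difference in Φ, the measure the plan already names, over the five rates. Test the 20 slopes with a one-sample t or Wilcoxon test, on the raw scale and on the log scale (log Φ on Sal minus log Φ on Exe). Claim a rate-dependent effect only if both scales agree.
3. State that this contrast is supportive only, because rate is confounded with time on hyperglycaemia and on exendin, and because an effect already present at the lowest rate cannot be separated from the glucose effect.

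The cost is a few sentences and one analysis of data already planned, with no change to the infusion schedule, visits, samples or sample size. The downside is a narrower primary claim, and a contrast whose precision depends on a between-step correlation that the documents do not give.

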**We will therefore address the following specific aim: -**

**Specific Aim:** Determine the contribution of GLP1R to glucagon-stimulated insulin secretion.

**1° Hypothesis:** Glucagon-stimulated insulin secretion is decreased by GLP1R blockade with exendin-9,39

**2° Hypotheses:** The contribution of GLP1R to glucagon-stimulated insulin secretion is more significant at higher glucagon concentrations

[figure not shown]

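### The plan gives two tests for its only primary hypothesis (one saline-versus-exendin comparison, and a comparison at each of five glucagon rates) and does not say which decides

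*Combined protocol and SAP*

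**What the plan says.** All of this is in the combined protocol and SAP. The primary hypothesis, under the specific aim, is directional and names no rate: "Glucagon-stimulated insulin secretion is decreased by GLP1R blockade with exendin-9,39".

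Section IV (Research Design and Methods) then describes its test in two ways.

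- **Statistical Analysis:** "A paired 2-tailed student *t*-test (parametric) or a Wilcoxon rank-sign test (non-parametric) will be used to examine differences between" the saline (Sal) and exendin (Exe) days, for the primary hypothesis. No rate is mentioned.
- **Interpretation:** "To test our 1° hypothesis, we will compare" Φ "during each glucagon infusion rate in the presence and absence of exendin-9,39". The next sentence turns to the secondary hypothesis: "we expect differences to be more marked at the higher glucagon infusion rates (2° hypothesis").

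Three other places in section IV bear on the choice.

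- **Study-day procedures:** "A glucagon infusion at 0.4ng/Kg/min will start at 0900 (0 min), increasing by 0.2ng/kg/min every hour", with saline or exendin-9,39 infused from 0 to 300 min.
- **Calculations:** the indices, Φ among them, are calculated "from the glucose, insulin and C-peptide concentrations observed during the experiments using the minimal model". Φ is the sum of a first-phase and a second-phase term. The text does not say how a separate Φ is obtained for each hourly step.
- **Table 1:** there is one row for the primary hypothesis, headed "1° hypothesis (n = 20 - paired"), with Φ 149 ± 45 and a detectable difference of 30 (20%). No rate, alpha or power is given.

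The Statistical Analysis and Power Calculation paragraphs refer to a Table 3. The only table in the text is labelled Table 1, and I take it to be the one meant.

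**The concern.** Two neighbouring paragraphs each claim to test the primary hypothesis, and they can disagree. A decrease at one glucagon rate with no significant overall difference would be support under the Interpretation sentence and no support under the Statistical Analysis sentence. With no rule fixed in advance, the choice could be made after the data are seen.

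The per-rate sentence cannot simply be assigned to the secondary hypothesis, because it names the primary one. Followed literally, without adjustment and with any one rate sufficing, it gives five chances of a false claim instead of one. The reader also cannot tell which comparison the 20% detectable difference describes.

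**Working it through.** **Inputs from the documents.** n = 20, paired; two-sided test; support means a decrease. The rate starts at 0.4 ng/kg/min and rises by 0.2 each hour over 300 min. That is 300/60 = 5 steps: 0.4, 0.6, 0.8, 1.0 and 1.2.

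**Assumed, because the documents do not state them.** Two-sided alpha of 0.05 per test, so 0.025 in the direction of a decrease; 80% power; the correlation between the five Exe − Sal differences; and the rule for combining the five results.

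**1. The plan's own figure.** Take 45 as the SD of the paired differences.

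- Standard error = 45/√20 = 10.06.
- Noncentrality for a difference of 30 = 30/10.06 = 2.98.
- By the noncentral t with 19 df, power for 30 is 80.7%, and the detectable difference at 80% power is 29.7. The stated 30 is reproduced.
- Table 1 does not say that 45 is the SD of differences. If it is the SD on one day, the SD of differences is 45 × √(2(1 − r)), which equals 45 only at a between-day correlation r = 0.5.
- At alpha 0.05/5 = 0.01 (Bonferroni for five tests), power for 30 with the same SD is 55.8%.

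So 30 (20%) behaves like the figure for one unadjusted paired test.

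**2. False support if any one of five decreases counts.** Under independence the chance is 1 − 0.975^5 = 0.119. For correlated differences, five paired t-tests with n = 20 were simulated under the null, with at least 200,000 trials per setting for the figures in this table:

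| Correlation | Equal between all steps | Decaying over steps (adjacent-step value) |
|---|---|---|
| 0.3 | about 11% | about 11% |
| 0.5 | about 9% | about 10% |
| 0.7 | about 8% | about 9% |
| 0.9 | about 5% | about 6% |
| 0.95 | about 4% | about 5% |
| 0.99 | about 3% | about 4% |

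One prespecified test gives 2.5%. If a significant difference in either direction counted, equal correlation of 0.3 to 0.9 gives about 21% to 10% (ceiling 1 − 0.95^5 = 0.226), against 5%.

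**3. Other rules.** If all five rates had to show a significant decrease, the risk is at most about 0.8% for correlations up to 0.9. With Holm across the five, a false decrease at any rate occurs in 2.4% to 1.2% of trials at correlation 0.3 to 0.9.

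**4. Is the mean of five per-step differences the quantity in Table 1?** Its SD is SD × √((1 + 4ρ)/5). With a per-step SD of 45:

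- ρ = 0.3: 45 × √(2.2/5) = 29.8, detectable difference about 19.7.
- ρ = 0.9: 45 × √(4.6/5) = 43.2, detectable difference about 28.5.

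Neither is 30, so a mean over steps is a different quantity and would need its own figure.

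**The case against.** The case for the single comparison is good. The only paragraph headed Statistical Analysis specifies Sal against Exe days. Table 1 has one primary row, and its 30 reproduces as one paired test. The primary hypothesis names no rate, whereas the secondary one concerns higher glucagon concentrations. The per-rate sentence stands under Interpretation, just before the secondary hypothesis, and could be read as describing how the data will be examined. All this stands, and it makes the single comparison the better-supported reading. It does not remove the conflict, because the Interpretation sentence says in terms that it is testing the primary hypothesis.

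The inflation figures are open to a second objection, which also stands. They need the per-rate reading, unadjusted tests and an any-rate rule together, and the documents state no combining rule. The five differences come from the same subject on the same two days, so a high correlation cannot be excluded, and 5% is not a floor.

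A reader might infer that the plan commits to five unadjusted tests, and so that its primary error rate is 11%, or that its power is only 56%. The documents support neither inference. They do not say that one rate suffices, and 56% would apply only if five tests were run at 0.01 each with an SD of differences of 45.

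**Conclusion.** The point holds as a conflict over which comparison decides the only primary hypothesis. That part rests on the text alone and needs no numerical assumption. The single-comparison reading is the better supported and carries no inflation.

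The size of the risk under the other reading is conditional. With two-sided 0.05 at each rate and any one decrease counting, false support runs from about 11% to about 5% for equal correlation of 0.3 to 0.9, with about 12% at independence and about 3% at 0.99. That compares with 2.5% for one test. Confidence is high in the conflict and lower in any particular figure. It should be settled before analysis.

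**What to change.** In the Statistical Analysis paragraph, name one Sal-versus-Exe test of Φ at two-sided 0.05 as the deciding test of the primary hypothesis. One Φ per study day is preferable, because it fits the Calculations paragraph and Table 1. Reword the Interpretation sentence so that the per-rate comparisons are Holm-adjusted follow-ups, and say how Φ is obtained for each hourly step. Use a treatment-by-rate contrast for the secondary hypothesis.

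State that Table 1's 30 (20%) refers to the deciding test, with its alpha, its power and whether 45 is the SD of differences, and correct the reference to Table 3. If the mean of the per-step differences is preferred as the deciding quantity, restate the detectable difference for it.

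The cost is a few sentences and a note to the table, with no change to subjects, visits or samples. The statistical price is that one overall test loses some power if the effect is confined to the highest rates, and that the adjusted follow-ups are less sensitive than unadjusted ones. For illustration only, take the mean over steps, a per-step SD of 45 and an effect rising linearly from 0 to 30. Power is then 57% to 31% at correlation 0.3 to 0.9, against 68% to 56% for Holm with any rate counting. If the investigators value that sensitivity more, they can make the per-rate tests primary, provided the plan says so in advance and states the adjustment.
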